4.6 Regulatory Status

The Surfacer System has been CE Marked and is commercially available in Europe. The Surfacer System is an investigational device in the United States.

5.0 BENEFIT/RISK ANALYSIS

5.1 Importance of CVA

Central venous access is vital to many patients with acute and chronic illness, being one of the most commonly performed procedures in medicine. Hemodialysis, fluid management, chemotherapy infusion and parenteral nutrition are examples of life-sustaining therapies that would not be possible

without CVA.

The indications for long-term venous access are widening and include the following:

[figure not shown]
[figure not shown]
[figure not shown]
[figure not shown]
- Cancer chemotherapy
- Long-term antibiotic therapy (e.g. infected prosthetic joints, bacterial endocarditis, cystic fibrosis)
- Parenteral nutrition (e.g., short bowel syndrome) hemodialysis
- Repeated blood transfusions
- Repeated venesection

The aim of CVA therapy is to position the catheter in a large vein to allow adequate dilution of infused products; reduced pain on injection; delay in the development of thrombosis; and aspirate blood.

There is increasing use of long-term central venous access devices, both in and out of hospital. Despite the apparent similarity between short and long-term access devices, there are important differences in design, usage and patterns of complication that are relatively specific to longer-term venous access.

Central venous catheters or CVCs are commonly inserted via the internal jugular, external jugular, subclavian, or femoral veins (**Table 8**).

Table 8: CVA Access Sites

	
Subclavian Access	Jugular Access
	 
Heart PICC line enters body here PICC

Femoral Access	Peripheral Inserted Central Catheter (PICC)

Catheter-related vein thrombosis is a recurrent problem with longer-term venous access devices. It is thought that thrombus starts at the site of the venipuncture and then migrates along the catheter to eventually occlude the tip. Such thrombus can be seen on ultrasound floating around the catheter within the vessel lumen, or as a ghost after catheter removal. Thrombus creates an obstruction to infusion of fluids and withdrawal of blood, and there is a strong link between thrombus and infection.

In a literature review conducted by Bluegrass Vascular Technologies, Acute Risks of mechanical complications during the CVA insertion procedure include arterial puncture, malposition, local hematoma, pneumothorax, hemothorax, air embolism, arrhythmias, accidental removal and failure of catheterization. Similarly, other mechanical complications are vessel perforation, atrial perforation and catheter malfunctions (Karkee, 2010)^{xxviii}. Table 9 displays safety rates for CVA insertion procedures via

subclavian and femoral routes.

Reported rates of arterial puncture are in the range of 1.3% - 4.2% for subclavian access, 2.2% - 7.5% for jugular access, and 2.4% - 4.3% for femoral access. The percentage of misplacement is between 0% - 3% in subclavian access, between 0% - 2.2% in jugular access, 0% in femoral access. In the articles analyzed the percentage of pneumothorax and hemothorax are reported respectively in a range of 0% - 3% and 0.04% in subclavian approach, 0% for both pneumothorax and hemothorax for the jugular and femoral access, 33% for both pneumothorax and hemothorax for the translumbar access. Mechanical complications are common in venous catheter insertion. The values reported are 6.5% for subclavian access, 5.8% for jugular access, between 3.6% and 14.3% for femoral access and between 8% and 21% for Translumbar access. The risk of Hematoma with the subclavian approach is 7.5%; jugular approach is between 1.0% - 12%; femoral approach is between 0% - 7.2%; and translumbar or transhepatic is between 0% - 4.5% (**Table 9**).

Long Term Risks after the placement of the CVA catheter include complications related to the permanence of the catheter such as infections, deep venous thrombosis, catheter colonization, and thrombotic complications. These complications are common for all types of Central Venous Access. Typical rates of infection are reported in a range of 0.4% - 29.3% for the subclavian access, 0.76 - 40% for the jugular access, 0.6% - 40.5% for the femoral access and 9.5% - 28% for the translumbar access. Thrombotic complications are reported for each access site examined, with values between 0.8% - 4.5% for the subclavian access, 4.3% - 22.7% for the jugular access, 2.4% - 12.7% for the femoral access and 3.2% - 33% for the translumbar access. Deep venous thrombosis values are reported in a range of 5.8% - 6.5% for the subclavian access, 0.5% - 12.8% for the jugular access, 0.5% - 8.9% for the femoral access and 16.7% for the translumbar access. Typical rates of catheter colonization are reported in a range of 1.4% - 4.9% for the subclavian access, 4.6% - 25.2% for the jugular access, 7.2% - 40.5% for the femoral access and 8% - 33.3% for the translumbar access.

In summary, although femoral vein cannulation has been reported as easier than subclavian or jugular, this vascular access type is associated with higher risk of mechanical complications and catheter colonization/infection compared to jugular and subclavian access.

Translumbar access sites are associated with the highest risk of complications compared to jugular, subclavian and transfemoral accesses. Indeed, the inferior vena cava access is preferred only when other accesses are occluded. Immediate hazards of translumbar access include retroperitoneal bleeding and inadvertent puncture of the right renal artery. Delayed complications include catheter migration and dislodgment, spontaneous retroperitoneal hemorrhage, and IVC stenosis progressing to chronic occlusion. Catheter erosion into the right ureter (ureteral fistula) has also been reported.

Translumbar central venous catheters should be used only for patients with no other option.

Table 9. Safety rates for Standard CVA Insertion Procedures

SUBCLAVIAN		Arterial Puncture		Misplacement		Pneumo-thorax		Hematoma		Hemothorax		Mechanical complications**	
Author	Year	Pts	%	Pts	%	Pts	%	Pts	%	Pts	%	Pts	%
Alexandrou E.	2014	2383	1.3%	2383	2.4%	238 3	0.4%		-	238 3	0.04%		-
Karkee D.V.	2010	203	3%	203	3%	203	0.5%		-		-	203	6.5%
Biffi R.	2009	-	-	136	0%	136	0%		-		-		-
Bertogli S	1996	424	4.2%		-	424	1.4%	424	7.5%		-		-
Smith H.O.	1995	133	3.8%		-	133	3%		-		-		-
FEMORAL		Arterial Puncture		Misplacement		Pneumo-thorax		Hematoma		Hemothorax		Mechanical complications**	
Author	Year	Pts	%	Pts	%	Pts	%	Pts	%	Pts	%	Pts	%
Hingwala J.	2014		-		-		-		-		-		-
Alexandrou E.	2014	163	4.3%	163	0%	163	0%		-	163	0		-
Yeral M.	2013		-		-		-	45	0%		-		-
Parienti J.J.	2008		-		-		-	370	1.1%		-		-
Lorente L.	2008		-		-		-		-		-	184	7.61%
Al-Hwiesh, A.K.	2007											14	14.3%
Montagnac R.	1997		-		-		-		-		-	55	3.63%
Bertoglio S.	1996	41	2.4%		-	41	0%	41	7.2%		-		-

**Mechanical complications include arterial puncture, malposition, local haematoma, pneumothorax, haemothorax, air embolism, arrhythmias, accidental removal and failure of catheterization. Similarly, other mechanical complications are vessel perforation, atrial perforation and catheter malfunctions (Karkee, 2010). Note: complication or data not analysed/mentioned in the articles are indicated with a dash (-).

5.2 Limitations of Available Treatments

Usually, when venous occlusion or thrombus fibrin formation occurs, the occluded vessel is difficult to access or deemed no longer patent or usable for long-term central venous access. Consequently, another access is required. Conventional methods for CVA in the presence of central venous occlusion have significant limitations, as described in **Table 10**.

Table 10: Conventional methods for central venous occlusion

Options	Therapeutic approach for CVA	Issues
Other upper body veins	When confronted with occlusion of a central vein, physicians usually utilize one of the remaining upper body veins (jugular and subclavian). The process can continue until all four central veins have been obliterated.	Loss of all four upper body central veins creates an access crisis leaving the patient without a central venous lifeline. When all four upper body central veins become occluded; physicians are forced to utilize alternative approaches that are much less desirable.
Femoral Veins Access	The femoral veins are utilized for long-term CVA when upper body sites are no longer available. Femoral veins are attractive secondary targets because they are relatively easy to access and, in most communities, the only option for central venous access when upper body sites have been exhausted.	Femoral venous catheters have poor stability due to leg movement, as well as high rates of infectious and thrombotic complications. Catheter migration, kinking and retraction are unique and common problems that result from leg movement. It is clear that the femoral veins are poorly suited to long-term central venous access. The use of femoral veins for long-term access can quickly lead to occlusions that eliminate a future route of temporary central venous access, further compounding the problem of lost central venous access.
Inferior Vena Cava access	Translumbar puncture of the inferior vena cava (IVC) is available in some tertiary care centers, but this procedure is technically challenging and carries significant risks. Translumbar central venous catheters should be used only for patients with no other option	Immediate hazards of translumbar access include retroperitoneal bleeding and inadvertent puncture of the right renal artery. Delayed complications include catheter migration and dislodgment, spontaneous retroperitoneal hemorrhage, and IVC stenosis progressing to chronic occlusion. Catheter erosion into the right ureter (ureteral fistula) has been reported.
Transhepatic access	Direct puncture of the liver can provide access to the inferior vena cava and right atrium via a hepatic vein. Due to poor catheter performance and	Transhepatic access is associated with substantial risks, and experience with the procedure is still limited. Serious complications include liver laceration, intra-peritoneal bleeding, and procedure-related death. Catheter instability due to respiratory

Options	Therapeutic approach for CVA	Issues
	very substantial hazards, transhepatic puncture for long-term central venous access should only be considered as a last resort	movement is a major problem. Catheter mobility also causes kinking, perforation, and related malfunctions that require catheter removal. Early thrombosis occurs much more frequently with transhepatic than with upper body catheters
Atrial access	Atrial access or surgical placement of catheters directly into the right atrium, has been described in a few patients who required life-sustaining nutritional support and had no alternative for vascular access. Isolated case reports describe right thoracotomy, median sternotomy, and video-assisted thoracic surgery to place catheters in the right atrium or the right atrial appendage.	Delayed complications of surgically-placed central venous catheters include catheter migration, dislodgment, infection, bleeding and pleural effusion. Thoracic surgery for placement central venous catheters is highly invasive and not easily repeated.
Occluded vessel recanalization	Recanalization of the occluded vessel, with placement of a new Central Venous Catheter, may allow recovery of the lost central venous access without involvement of other veins. Scientific literature describes this method as “sharp recanalization” : the distal sharp tip of a catheter is forced to cross the occluding thrombus. A fluoroscopic target is placed on the other side of the occlusion, requiring a second skin entry point. After the thrombus is crossed, a loop is introduced to catch and pull a new Central Venous Catheter inside the vessel.	The sharp recanalization procedure is complex and not standardized. It often requires new transcutaneous accesses both from the femoral vein and from the occluded vein, more distally than the previous access location. There is no single device that has been developed to perform this procedure, although the Outback and Rosh-Uchida catheters have been used “off label” to perform the procedure.

5.3 Clinical Considerations

Upper body veins are always preferred for long-term central venous access. Devices placed via upper body veins provide the best combination of patient comfort and mobility, device stability, accessibility, and infection risk. When the upper body central veins are lost, the remaining alternatives are undesirable for anything but emergency, temporary access. Central venous catheterization can be obtained with access from sites other than the jugular or subclavian veins, but with major short and long-term complication rates. Advantages and disadvantages of the available access routes are summarized in **Table 11**.

Table 11: Advantages and disadvantages of different routes for CVA

CV Catheter Insertion Route	Advantages	Disadvantages
Arm veins (cephalic, basilic)	Simple to access, veins visible and palpable No vital organs close Patient comfort	Failure to achieve central position High incidence of thrombosis Low maximum infusion rates
Internal jugular	Simple to insert Direct route to central veins High flow rate, low risk of thrombosis Lower risk of pneumothorax	Patient discomfort Higher rate of late complications, especially infection Tunnelling more difficult to chest wall
Subclavian axillary	Less patient discomfort Lower risk of long-term complications	Curved insertion route Difficult to access Acute complications - pneumothorax, haemothorax, nerve damage
Femoral	High flow, good for dialysis Easy insertion	Higher rate of infection and thrombosis Poor stability: migration, kinking, retraction Patient discomfort Difficult in obese patients
Inferior Vena Cava (Translumbar)	Last option procedure	Technically challenging Procedural risks: retroperitoneal bleeding, renal artery puncture Migration, Dislodgement, Occlusion

5.4 Surfacer System Potential Benefits

As described in **Table 11**, the innovative approach of the Surfacer System brings advantages to patients that no longer have adequate access or who cannot achieve CVC using conventional approaches to central venous catheterization.

The potential benefits of the Surfacer System IOCVA approach include but are not limited to the following:

- **Reduction of Insertion Risk**

Reversing the path to venous access is intended to avoid or reduce risks of damage or involvement of other anatomical structures, such as arterial puncture (with edema or serious bleeding), lung injury (i.e. pneumothorax or hemothorax) or nerve damage.

- **Ease of Procedure**

The aiming features using the Exit Target, specifically developed for fluoroscopy, allow precise needle positioning and accurate delivery to the skin surface. The simplicity of the procedure, which requires placing the ring at planned CVC exit, makes it attractive and suitable for clinical application in the larger treatment population.

- **Ability to Cross Occlusions**

The Surfacer System may be able to create central venous access in subjects with prior multiple occlusions or who have no other options.

- **Ability to Spare Other Vessels**

The Surfacer System may be able to utilize a previously occluded vessel and spares /salvages other vessels for physiological circulation and other access requirements. In emergent situations, this could be a lifesaving benefit to patients who have few or no other options for venous access.

THE SURFACER SYSTEM APPROACH HAS DEMONSTRATED THE FOLLOWING BENEFITS:

- low patient risk
- quick and safe procedure
- **solution for Central Thoracic Veno-Occlusive Diseases** in no option cases, with the potential to achieve repeated access from a single point
- success in patients with no upper body access
- preserve jugular vein access

5.5 Surfacer System Potential Risks

Potential risks associated with using the Surfacer System are considered to be similar those associated with routine interventional procedures and with the patient's underlying condition. List of Potential Risks and Definitions can be found in Appendix A.

These potential risks include, but are not limited to:

- Pain
- Infection
- Bleeding
- Adverse tissue reaction; allergic reaction
- Cardiovascular sequelae including: perforation, tamponade, spasm or effusion
- Lymphatic system sequelae
- Pulmonary sequelae including: pneumothorax, pulmonary embolism
- Vascular sequelae including vasospasm, vessel perforation, dissection, or aneurysm
- Unintended embolization or thrombosis
- Arrhythmias
- Neurologic sequelae including stroke; transient ischemic attack; nerve injury
- Arteriovenous Fistula
- Death
- Surfacer System component failure or malfunction

5.6 Benefit/Risk Statement

The Surfacer System is intended to provide a solution in patients with an upper body venous occlusion or other thrombotic fibrin occlusive pathology impeding standard access methods, including contraindication to use of remaining veins.

The Surfacer System is designed to allow Central Venous Catheterization utilizing an inside-out approach. This approach brings benefits to patients with CV occlusion, in whom alternate access options (conventional access methods) are not feasible or are associated with high risk and morbidity.

This new reversed approach brings expected benefits to patients in whom alternate access options are not feasible or associated with high risks. Expected benefits include: reduction of insertion risk; ease of

procedure thanks to the use of a visible exit target, enabling precise aiming of the needle; ability to overcome occlusions in subjects with limited or no other options; and ability to spare other vessels.

The Surfacer System approach to CVA catheterization provides visual and placement (steering) benefits that cannot be achieved with conventional approaches in patients with central vein occlusions.

Additionally, the Surfacer System device provides access to occluded veins, using the same vessel that was lost for CVA. Preclinical verification and validation of the Surfacer System and clinical experiences demonstrate safety and effectiveness of the Surfacer System procedure.

The Surfacer System is not associated with long-term risks, because the device is for temporary use. However, the Surfacer System allows CVA catheters to be successfully placed for short-term and long-term use. Therefore, it is important to analyze and compare the immediate procedural risks of other conventional approaches in patients with central vein occlusions in order to determine the risk reduction that is achieved with the Surfacer System approach.

The Inside-Out approach, based on reversing the path to venous access, has shown the capability to avoid or reduce the reported clinical risks of damage or involvement of other anatomical structures, such as arterial puncture (with edema or even serious bleeding), lung injury (i.e. pneumothorax or hemothorax) or nerve damage. No such events were observed in a large series of over 124 patients who underwent this procedure as well as the 12 patients in the first in human study.

The scientific literature and human clinical experience finds that the Surfacer System provides stable, upper body central venous access that is suitable for any conventional catheter. Therefore, based on the current evidence and testing, the benefits of use of the Surfacer System outweigh the risks in the defined patient populations.

Central venous occlusions place patients at significant clinical risks, including:

- Cerebral edema, which puts patients at risk for chronic memory loss, learning deficiency, and possible MS linkage
- Current standard of care “outside-in” approach increases the risk of significant puncture, rips and tears to arteries, lungs, and other critical systems
- Increased infection risk once jugular veins are obliterated and access is shifted to the use subclavian and femoral access sites

6.0 STUDY DESIGN

This study has been designed as a prospectively enrolled, single-arm, multicenter study to demonstrate the safety and efficacy of the BVT Surfacer System in patients who require central venous access.

A total of 30 subjects is planned at a minimum of three (3) sites. Ten subjects will be enrolled initially. After safety data review, enrollment is expected continue to 30 subjects overall with no more than 10 subjects enrolled at a single site.

Enrolled subjects will undergo the Surfacer System procedure, then exit the study after follow-up at hospital discharge and 7-days post procedure. BVT will utilize an Independent Data Monitoring Committee (IDMC) to review the study’s safety data during the conduct of the study and at study closure.

6.1 ASA Guidelines

The study, designed in conformance with the standard of care for central venous access, as defined by the American Society of Anesthesiologists Task Force on Central Venous Access. *Anesthesiology*, 2012 Mar; 116(3):539-73. ^{xxix} These guidelines define central venous access as placement of a catheter such that the catheter is inserted into a venous great vessel. The venous great vessels include the superior vena cava, inferior vena cava, brachiocephalic veins, internal jugular veins, subclavian veins, iliac veins, and common femoral veins.

6.2 Subject Selection and Participation

The study population include patients who are candidates for vascular access with limited or diminishing upper body venous access or pathology impeding standard access methods (see Inclusion Criteria #3,

section 6.3.1).

Subjects who provide informed consent will undergo screening and baseline assessments. Subjects who successfully pass the inclusion and exclusion criteria will undergo the Surfacer System procedure, with subsequent follow-up assessments at hospital discharge and 7 days post procedure.

6.3 Study Eligibility Criteria

To qualify for study participation, subjects must meet all of the Inclusion Criteria and none of the Exclusion Criteria.

6.3.1 Inclusion Criteria

1. Subjects are between 18-80 years of age.
2. Subjects referred for placement of a central venous access catheter.
3. Subjects have limited or diminishing upper body venous access or pathology impeding standard access methods.
4. Subjects are willing and able to give written informed consent.

6.3.2 Exclusion Criteria

1. Subjects are contraindicated for Surfacer System use if one of the following are found (per the IFU):
 - a. Occlusion of the right femoral vein;
 - b. Occlusion of the right iliac vein;
 - c. Occlusion of the inferior vena cava.
2. Subjects contraindicated for central venous access based upon the treating physician's opinion and institutional standard of care.
3. Subject has acute thrombosis within any vessel (SVC, jugular, inferior vena cava (IVC), brachiocephalic and subclavian) planned to be crossed by Surfacer System.
4. Subject has tortuous anatomy which precludes a straight line from femoral venous entry to subclavian exit.
5. Subject has been diagnosed with active pericarditis or endocarditis.
6. Subject has a known or suspected pericardial effusion.
7. Subject has a known or suspected aneurysm or ectasia of ascending aorta, innominate artery, or subclavian artery.

8. Subjects who are pregnant or of childbearing potential not taking adequate contraceptive measures or nursing during the study.

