Exclusion Criteria	
 1. Subjects are contraindicated for Surfacer System use if one of the following are found (per the IFU): 
 a. Occlusion of the right femoral vein; b. Occlusion of the iliac vein; c. Occlusion of the inferior vena cava. 2. Subjects are contraindicated for central venous access based upon the treating physician's opinion and institutional standard of care. 3. Subject has acute thrombosis within any vessel (SVC, jugular, inferior vena cava (IVC), brachiocephalic and subclavian) planned be crossed by Surfacer System. 4. Subject has tortuous anatomy which precludes a straight line from femoral venous entry to subclavian exit. 5. Subject has been diagnosed with active pericarditis or endocarditis. 6. Subject has a known or suspected pericardial effusion. 7. Subject has a known or suspected aneurysm or ectasia of ascending aorta, innominate artery, or subclavian artery. 8. Subjects who are pregnant or of childbearing potential not taking adequate contraceptive measures or nursing during the study.

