3.3 Principles and Mode of Operation

The Surfacer System uses the same principle technique as conventional CVA procedures, by tunneling through or bypassing the occlusion, but does this in the reverse direction, from the inside to the outside. With the Surfacer System, the Surfacer Device is percutaneously introduced into the right femoral vein. It is advanced up the inferior vena cava, via the superior vena cava (SVC), to the location of the occlusion. When the occlusion has been visualized under fluoroscopy, a needle wire is oriented to advance through or to bypass the occlusion and to exit to a pre-determined external target. A new central venous catheter is then back-loaded into the Peelable Introducer and positioned below the occlusion. Placement of the central venous catheter below the venous occlusion restores central venous access.

Prepare the right femoral and right sub-clavicular area for sterile percutaneous access. Administer conscious sedation and local anesthesia according to hospital protocol. Follow standard access procedures to gain access into the femoral vein using .035" x 150-180 cm J-tip exchange guidewire.

Advance the Workstation Sheath and dilator over the exchange wire to the venous occlusion. Once the location of the Workstation Sheath is in the occlusion as confirmed by injecting a small bolus of contrast, place an Exit Target to the exit point supraclavicular and proceed with insertion of the Surfacer Device through the Workstation Sheath. Once positioning is confirmed the Handle can be used to advance the Needle wire out of the needle guide and exit the skin. For Type III and Type IV occlusions, inject a small bolus of 5-10cc of contrast through Workstation sidearm to exclude extravasation of contrast under fluoroscopy into the pleural or pericardial space. If visualization cannot be confirmed a 4 or 5F sheath could be back loaded over the Needle wire and injection of contrast could be performed under a gently pull back to opacify the tract of exit is free from extravasation. Once confirmed, the Peelable Introducer can now be back loaded over the exiting wire and access can be confirmed by fluoroscopy. Upon completion of the procedure, a desired CVA catheter can be exchanged or introduced adjacent to the Peelable Introducer.

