3.4 Contraindications

The Surfacer System is contraindicated for patients with an occlusion of the right femoral vein, iliac vein

or inferior vena cava, or acute thrombosis within a vessel to be crossed by the Surfacer System. Special precautions may be required for patients with coagulation disorders and patients on anti-coagulation therapy.

The Surfacer System is not intended for use in the coronary or cerebral vasculature.

This device is not to be used in the arterial system.

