7.2 Screening and Baseline Assessments

Screening and Baseline assessments will include the following:

- Inclusion and Exclusion Criteria

- Medical history with demographics
- Physical exam with vital signs
- TCVO Lesion Type Determination
- Medications (antithrombotic and cardiovascular)
- Pregnancy test (not required if patient is male or non-child bearing potential)
- Clinical laboratory tests including coagulation profile (APTT, PT, INR), CRP, LDH, ASAT, ALAT, fibrinogen, D-dimer
- Ultrasound or venous duplex venography of upper body veins (SVC, jugular, inferior vena cava (IVC), brachiocephalic and subclavian) to rule out acute thrombosis within a vein to be crossed by the Surfacer System
- AP and LAT chest x-ray or cine fluoroscopy will be performed prior to the procedure to define the pattern of occlusion and to rule out acute thrombosis
- 12-lead ECG

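### The vessel list in exclusion 3 and in the baseline scan omits the femoral and iliac veins on the device's route, so non-occlusive acute thrombus there is ambiguous and no scheduled test names those veins

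*Combined protocol and SAP*

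**What the plan says.** Section 3.4 (Contraindications) rules out use of the device where there is "acute thrombosis within a vessel to be crossed by the Surfacer System". It lists no vessels for this rule, and it states occlusion of the femoral, iliac and inferior caval veins as a separate contraindication.

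Section 3.3 (Principles and Mode of Operation) gives the route: "the Surfacer Device is percutaneously introduced into the right femoral vein. It is advanced up the inferior vena cava".

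Exclusion 3 in Section 6.3.2 reads: "Subject has acute thrombosis within any vessel (SVC, jugular, inferior vena cava (IVC), brachiocephalic and subclavian) planned to be crossed by Surfacer System". The synopsis (Section 1.1) carries the same five-vessel bracket: "Subject has acute thrombosis within any vessel (SVC, jugular, inferior vena cava (IVC), brachiocephalic and subclavian) planned be crossed by Surfacer System".

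Section 7.2 sets the matching baseline test: "Ultrasound or venous duplex venography of upper body veins (SVC, jugular, inferior vena cava (IVC), brachiocephalic and subclavian) to rule out acute thrombosis". The sentence then goes on to state the purpose in terms of veins that the device will cross.

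Exclusion 1 does name the access veins, but only for occlusion. Item 1a in Section 6.3.2 is "Occlusion of the right femoral vein", and item 1b applies the same word to the iliac vein.

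**The concern.** The list includes the inferior vena cava, which lies on the way up, but skips the two segments that the device passes before reaching it. An investigator who works through exclusion 3 by its bracket would not count a fresh, non-occlusive thrombus in the right femoral or iliac vein as an exclusion, although Section 3.4 contraindicates the device in that subject. A sonographer who scans the vessels listed in Section 7.2 would not look there.

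The protocol's own background makes the question a fair one for this population. Subjects are people whose upper body access is running out. Section 5.2 says that the femoral veins are used once upper body sites are exhausted, and that such use can lead quickly to occlusion. Section 5.5 lists pulmonary embolism and unintended embolization as potential risks. Section 9.1.2 makes the Section 5.5 list part of the anticipated adverse events, which the second primary safety endpoint counts.

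**Working it through.** No formula applies and the plan gives no figure to reproduce. The check sets the route beside each rule and each test.

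**Step 1: the eligibility rules.**

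| Segment on the route (3.3) | Contraindicated if acutely thrombosed (3.4) | Named in exclusion 3 (1.1 and 6.3.2) | Named in the 7.2 scan | Covered by exclusion 1 |
|---|---|---|---|---|
| Right femoral vein | Yes, it is crossed | No | No | Occlusion only (1a) |
| Iliac vein | Yes, it is crossed | No | No | Occlusion only (1b) |
| Inferior vena cava | Yes | Yes | Yes | Occlusion only (1c) |
| Superior vena cava and the upper body veins crossed | Yes | Yes | Yes | No |

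The iliac vein is not named in 3.3, but a device that goes from the femoral vein to the inferior vena cava must pass through it. Section 3.4 treats occlusion and acute thrombosis as separate conditions, so exclusion 1 cannot be assumed to cover a thrombus that does not occlude.

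**Step 2: the tests before and during access.**

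- Ultrasound or duplex (7.2): described as a scan of upper body veins, with the five-vessel bracket. The row in the Schedule of Assessments (1.3) names the test and lists no vessels.
- Chest X-ray or cine-fluoroscopy at baseline (1.3 footnote 4, and 7.2): said to help rule out acute thrombosis. The femoral and iliac veins are not mentioned.
- Intra-procedural venography (7.4): its stated purpose is to confirm occlusions.
- Contrast bolus in 3.3: confirms that the Workstation Sheath is in the occlusion, which is after the femoral and iliac veins have been passed.

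No scheduled pre-procedure assessment names the femoral or iliac veins. That holds for acute thrombosis and also for the occlusions in exclusions 1a and 1b.

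**Step 3: how a case could reach the analysis.**

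- Under Section 7.3 a subject is enrolled once a component of the study device is inserted. Before that, an unsuitable subject is a screen failure (7.2.1).
- Section 3.3 passes an exchange guidewire before the Workstation Sheath. An obstruction that stops the wire is thus found before enrolment and enters no denominator. One found after the sheath is in belongs to an enrolled subject.
- Pulmonary embolism and embolization are not components of the acute safety composite (6.4.2). They would count there only through a listed component such as intensive care transfer, resuscitation or death. They can count directly under the second primary safety endpoint.
- One subject in 30 is 1/30 = 3.3 percentage points. This is true of any single event in a study of this size and does not measure this gap.

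**Step 4: can it be sized?** Section 5.1 cites thrombotic complications of 2.4% to 12.7% and deep venous thrombosis of 0.5% to 8.9% with femoral access. These are complications of catheters placed by that route, not the prevalence of acute right femoral or iliac thrombus at screening. The documents give no such prevalence, so no expected number of affected subjects can be calculated.

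**The case against.** The strongest reply is that exclusion 3 turns on the words before and after its bracket. It speaks of any vessel that the device is planned to cross, which is the same test as Section 3.4, and it does not say that the bracket is exhaustive. The Section 7.2 sentence ends with the same purpose. It also places the inferior vena cava among upper body veins, which suggests a loosely drafted list rather than an exact definition. Section 3.5 requires investigators to know the contraindications in the Instructions for Use before using the device, so a site that knew of a femoral or iliac thrombus would have to disregard 3.4 in order to proceed. Exclusions 1a and 1b already remove thrombus that occludes the right femoral or right iliac vein.

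Most of this stands, and it limits the point. A reader might infer that a subject with acute femoral or iliac thrombus is plainly eligible. The documents do not support that: it is one of two readings, and it concerns non-occlusive thrombus only. A reader might also infer that sites would not look. That cannot be said either, because detailed preparation and use are left to the Instructions for Use, which are not part of these documents. Nor do the documents support a claim that either primary rate would shift by a known amount.

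The reply does not supply a test. A broad reading of exclusion 3 helps only if someone images the veins, and the scan in 7.2 carries the same bracket as the exclusion.

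**Conclusion.** The point holds as an ambiguity and a screening gap. Exclusion 3, in both places, and the 7.2 scan list five vessels and omit two segments that every procedure crosses as Section 3.3 describes it. Whether a non-occlusive acute thrombus in those segments is excluded depends on how the bracket is read. No scheduled pre-procedure assessment names imaging of these veins, even though exclusions 1a and 1b depend on their state.

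It is worth correcting because it concerns subject safety and is cheap to put right, but it does not decide whether the trial can answer its question. No sample size, confidence interval or endpoint figure changes. The conclusion assumes that access is through the right femoral vein, as 3.3 states, and that nothing outside these documents already specifies femoral and iliac imaging. It is separate from the difference in iliac wording between the synopsis and Section 6.3.2, and from the timing of the scan.

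**What to change.** The sponsor should reconcile four places so that they state one rule: Section 3.4, exclusion 3 in the synopsis, exclusion 3 in Section 6.3.2, and the scope of the ultrasound/duplex in Section 7.2, each read against the route in Section 3.3. The protocol should also state which scheduled assessment supports exclusions 1a, 1b and 3. Which rule governs is for the sponsor to decide. If 3.4 governs, the vessel lists and the scope of the scan should match the full route.

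The cost is wording edits in the synopsis, 6.3.2 and 7.2. If the scan's scope is widened, an examination that is already scheduled will take somewhat longer; the documents do not say by how much. There may be an occasional extra screen failure, among subjects whom Section 3.4 already contraindicates. The analysis plan needs no change.
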